14.4 Analysis of Secondary Endpoints

The incidence of side effects associated HLA-B27-associated uveitis, such as cystoid macular edema (central 1 mm subfield thickness), keratopathy and synechia, will be compared between treatment groups using logistic regression. In addition, the changes in IOP, in central 1 mm subfield thickness will be compared between treatment groups using ANCOVA, with the baseline level included in the model. The presence of keratopathy and synechiae will be compared between treatment groups using logistic regression. The number of quadrants involved by synechiae, when present, will be described.

The changes in BCVA and symptoms (ocular pain, blurred vision, floaters and photophobia), measured by VAS, will be compared between treatment groups using ANCOVA, with the baseline level included in the model.

Each information collected through the Quick questionnaire will be compared between the two treatment groups using chi-square test.

14.5 Safety Evaluations

Safety and tolerability data will be summarized by treatment group.

Clinical evaluations for safety and tolerability assessments will include monitoring AEs, vital signs, concomitant medications and compliance.

Adverse event will be coded using the last updated version of the Medical Dictionary for Regulatory Activities (MedDRA) dictionary to give a preferred term (PT) and a system/organ class term (SOC) for each. Adverse events will be tabulated by treatment group. Tables will include the number of patients who experienced at least one AE, of study product-related AEs (defined as definitely, probably, possibly, or unrelated), of serious AEs, and the number of patients withdrawn due to AE, summarized by treatment arm. Comparisons between treatment arms will be performed using chi-square test.

Concomitant medications will be summarized by treatment using descriptive statistics and they will be listed.

Vital signs will be summarized by treatment using descriptive statistics for absolute values and change from baseline.

Compliance to the study treatment will be assessed through the patient diary and checked versus the used and unused study product containers given back by the patients.

14.6 Interim Analysis

No interim analysis planned.

14.7 Sample Size

In a previous study²⁵, 275 relapses on 106 patients were observed, corresponding to a mean number of relapses per patient of 2.6 (Standard deviation, SD: 0.7) while in the post-treatment group 36 relapses were registered corresponding to a mean number of relapses per patient of 0.34 relapses/patient. With a statistical power of 80% and a significance level (alpha) of 5% and a common SD of 0.7, 46 patients are needed to observe a difference of 0.6 relapses/patients between the two treatment groups (i.e., 2 relapses/patient in the NORFLO[®] ORO treatment group vs. 2.6 in the placebo treatment group). To take into account a potential dropout rate of 20% over 12 months, 60 patients will be recruited. Subjects dropping out the study because they are beginning systemic therapy with anti-inflammatory, immunosuppressive, biologic drugs will be replaced.

A second primary endpoint, i.e. the reduction of mean number of relapses between the year before treatment and the study period, will be examined. No formal sample size estimate is feasible on this endpoint, as it was not tested previously and no reasonable scenario can be drawn.

As the two endpoints will be assessed in a hierarchical order (first, "the mean number and intensity of relapses during the study between treatment groups" and then "the reduction of mean number of relapses between the year before treatment and the study period"), according to the "Points to consider on multiplicity issues in clinical trials", issued by the Committee for Proprietary Medicinal Products (CPMP - 2002), no sample size adjustment for multiplicity is needed.

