Colorectal tumor-bearing mice with oxaliplatin-resistant cells were treated with Meriva[®] alone and in combination with oxaliplatin. Oxaliplatin-resistant HCT116 p53wt and p53(-/-) cell lines were generated and the effects of oxaliplatin in combination with curcumin on resistance- and proliferation-associated proteins investigated. Eighty nude mice were implanted with HCT116 p53wt colorectal cancer cells before randomization into the following treatment groups: control, Meriva only, oxaliplatin only, Meriva[®] + oxaliplatin. Meriva[®] in combination with oxaliplatin was able to decrease the proliferative capacity of oxaliplatin-resistant p53wt and p53 (-/-) cell lines more effectively than oxaliplatin alone. Meriva[®] in combination with oxaliplatin also decreased expression of markers associated with cell proliferation. After 21 days of treatment in the xenograft model, the order of treatment efficacy was $Meriva^{\mathbb{R}} + oxaliplatin > Meriva^{\mathbb{R}} > oxaliplatin > control.$ The decrease in tumor volume when compared to vehicle-treated animals was 53, 35 and 16%, respectively. Meriva[®] did not adversely affect the DNA-platinating ability of oxaliplatin. On the other hand, curcumin enhanced the cytotoxicity of oxaliplatin in models of oxaliplatin resistance in vitro. In vivo, Meriva greatly enhanced oxaliplatin efficacy, without affecting the mode of action of oxaliplatin. Therefore, addition of formulated curcumin to oxaliplatinbased chemotherapy regimens has the potential for clinical benefit in colorectal cancer²⁴.

1.5 **Overview of Clinical Studies**

The efficacy and tolerability of curcumin-complex was evaluated as an adjunctive therapy to traditional treatment. Curcumin-phosphatidylcholine complex (Meriva[®]/NorFlo) was administered twice a day in recurrent anterior uveitis of different etiologies. The study group consisted of 106 patients who completed a 12-month follow-up therapeutic period. The patients were divided into three main groups based on the uveitis origin: group 1 (autoimmune uveitis), group 2 (herpetic uveitis), and group 3 (different etiologies of uveitis).

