14.3 Analysis of Primary Endpoint

The number and intensity of relapses will be assessed through instrumental analysis and physical examination. These endpoints will be assessed from baseline to end of treatment.

Mean and standard deviation will be used to describe the number of relapses per patient. The mean number of relapses per patient will be compared between the treatment groups using Student's t-test. ANOVA will be used to include predictive/confounding variables in the model.

In addition, a generalized linear mixed model (GLMM) with Poisson statistical distribution and with the number of relapses as dependent variable will be used to assess the effects of the treatment on reducing the number of relapses, also including in the model other potentially predicting/confounding variables.

The intensity of relapses will be scored as mild (either trace to 1+ cell OR flare \leq 20), moderate (2+ to 3+ cell OR Flare > 20 and < 100) and severe (4+ cell OR Hypopyon OR flare \geq 100). For each patient, the average intensity will be estimated as the mean of the intensity observed during each relapse. The average and the maximum intensity will be compared between treatment groups using Student's t-test. ANOVA will be used to include predictive/confounding variables in the model.

The mean number of relapses per patient observed during the study will be compared to the mean number of relapses reported the previous year within each treatment group using paired t-test or ANOVA, to eventually adjust for predictive/confounding variables. As group means can be somewhat deceptive with small number of events, the patients will be classified based on the number of relapses before treatment and then on the number of relapses after treatment. The number of patients that change class before and after treatment (for example, from a high number of relapses to a low number) will be described and compared between treatment groups.

The primary efficacy endpoints will be analyzed in the following hierarchical order: first, "the mean number and intensity of relapses during the study between treatment groups" and then "the reduction of mean number of relapses between the year before treatment and the study period".

The level of cell damage and inflammation will be assessed through Laser Flare Meter. The difference between treatment groups will be compared using ANCOVA, with the baseline level included in the model.

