### 4.3 Randomization and Blinding

Up to 60 eligible patients were randomly assigned to NORFLO® ORO or placebo treatment groups in a 1:1 ratio rusing a stratified randomization-blocks-scheme. The patient randomization list was generated-by-Latis S.r.l., using the procedure PROC PLAN of SAS 9.4 for Windows (SAS Institute Inc., Cary, NC, USA).

Due to the objectives of the study, the investigators, research staff, or patients did not know the treatment identity (test or control). The following study procedures were in place to ensure double-blind administration of study treatments:

Access to the randomization code was strictly controlled.

Packaging and labeling of test and control treatments were identical to maintain the blind.

The study blind will be broken on completion of the clinical study and after the study database has been locked.

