### 5. STUDY ENDPOINTS

### 5.1 Primary Endpoints

The primary efficacy endpoint is the mean number and intensity of relapses per patient occurred during the study, from baseline to end of treatment, in patients treated with the NORFLO® ORO compared to patients treated with placebo.

The reduction in relapses was determined by a reduction of the intraocular inflammation through a clinical and diagnostic evaluation that includes Laser measurement of AC flare with Kowa LFM 600 or LFM 700 (Normal range 2.5-7 ph/ms, Outside normal range > 10 ph/ms).

The reduction of the mean number of relapses per patient between the year before treatment and the study period within each treatment group will also be assessed.

The reduction of cell damage and inflammation were measured by the Laser Flare Meter, in patients affected by HLA-B27-associated uveitis after treatment with NORFLO® ORO, when compared to placebo.

The number and intensity of relapses and LFM data, used in primary efficacy endpoints, were reported in the first unscheduled visit.

Only patients with relapses will be analyzed in primary efficacy endpoints.

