# 7. SAMPLE SIZE AND STATISTICAL POWER CONSIDERATION

With a statistical power of 80% and a significance level (alpha) of 5% and a common SD of 0.7, 46 patients are needed to observe a difference of 0.6 relapses/patients between the two treatment groups (i.e., 2 relapses/patient in the NORFLO® ORO treatment group vs. 2.6 in the placebo treatment group). To take into account a potential dropout rate of 20% over 12 months, 60 patients were recruited.

A second primary endpoint, i.e. the reduction of mean number of relapses between the year before treatment and the study period, will be examined. No formal sample size estimate was feasible on this endpoint, as it was not tested previously and no reasonable scenario can be drawn.

As the two endpoints will be assessed in a hierarchical order (first, "the mean number and intensity of relapses during the study between treatment groups" and then "the reduction of mean number of relapses between the year before treatment and the study period"), according to the "Points to consider on multiplicity issues in clinical trials", issued

Statistical Analysis Plan Version no. 1.0 – 20/07/2020 Protocol Code NORFLO-ORO-16 EudraCT number NA

by the Committee for Proprietary Medicinal Products (CPMP - 2002), no sample size adjustment for multiplicity was needed.

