#### Multicenter Studies Considerations 9.2

Analysis will be adjusted for the clinical site. Analyses specific for each clinical site will be considered, based on the number of subjects enrolled in each clinical site.

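### The trial is sized on SD 0.7, but the additional Poisson model for the same relapse counts implies SDs of at least 1.41 and 1.61, so at SD 0.7 its standard errors would be about twice too wide (minor)

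*Protocol*

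**What the plan says.** Protocol 14.7 and SAP 7 give the same calculation: "With a statistical power of 80% and a significance level (alpha) of 5% and a common SD of 0.7, 46 patients are needed" for 2.0 relapses per patient on active treatment against 2.6 on placebo. SAP 7 adds the allowance for loss: "dropout rate of 20% over 12 months, 60 patients were recruited". Protocol 14.7 takes the placebo mean and the SD from a previous study with 275 relapses in 106 patients, "corresponding to a mean number of relapses per patient of 2.6 (Standard deviation, SD: 0.7", and uses that SD in both arms.

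For the analysis, Protocol 14.3 and SAP 11.4.1 list Student's t-test first, with ANOVA for covariates. Both then add "a generalized linear mixed model (GLMM) with Poisson statistical distribution and with the number of relapses as dependent variable". The summary table in SAP 11.5 puts all three methods in one row for this primary endpoint.

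Neither document names a dispersion or scale parameter, robust standard errors, or a check of variance against mean. Neither names a random effect for the mixed model; SAP 9.2 says only "Analysis will be adjusted for the clinical site". The distributional fallback in SAP 11 and SAP 13 is a non-parametric test, which does not touch the model's standard errors. Protocol 14.3 and SAP 11.4.1 mention no confidence interval.

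**The concern.** A Poisson count has a variance equal to its mean. The planning SD gives a variance well below the planned means, so the sample size and the additional model make incompatible statements about the spread of one endpoint, and no text reconciles them.

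If the planning SD is right, a model that fixes the variance at the mean overstates its uncertainty. Two planned analyses of the same primary count could then disagree: a clear t-test result beside an unconvincing rate ratio. No section says how to read that. A reader who trusts the count model more, because the data are counts, would be misled about the precision reached.

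**Working it through.** **Inputs.** Means 2.0 and 2.6, common SD 0.7, alpha 5%, power 80%, 46 evaluable and 60 recruited (Protocol 14.7, SAP 7); 1:1 allocation (Protocol 8.1). Sidedness is not stated. Two-sided is assumed because it reproduces the stated number; a one-sided normal approximation gives 34.

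**Reproducing the plan.** The standardised difference is 0.6/0.7 = 0.857. A two-sided t-test needs 22.4 per arm, hence 23 per arm or 46 in total, with 81.1% power (90.4% with 30 per arm). For dropout, 46/0.8 = 57.5, so 60 is enough. The sizing has no arithmetic error.

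**Spread implied by the Poisson model.** SD = √mean.
- Active: √2.0 = 1.41. Placebo: √2.6 = 1.61.
- The planning variance is 0.7² = 0.49, which is 0.49/2.0 = 25% and 0.49/2.6 = 19% of the means.
- A random effect adds variance to a Poisson count, so 1.41 and 1.61 are minimum values and no random effect can bring them down to 0.7.

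**Standard error of the log rate ratio, n per arm.**
- Variance fixed at the mean: √(1/(2.0n) + 1/(2.6n)) = 0.196 at n = 23 and 0.172 at n = 30.
- Actual value at SD 0.7 (delta method): √(0.49/(4n) + 0.49/(6.76n)) = 0.092 and 0.081.
- Ratio: 0.196/0.092 = 2.1.

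**Results if the observed means equal the planned ones and SD is 0.7.** The log rate ratio is ln(2.0/2.6) = −0.262, a rate ratio of 0.77. The t statistic is 0.6/(0.7√(2/n)).

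| | 46 patients | 60 patients |
|---|---|---|
| t-test p | 0.006 | 0.002 |
| Poisson test p, variance fixed at mean | 0.18 | 0.13 |
| Rate ratio 95% CI, variance fixed at mean | 0.52–1.13 | 0.55–1.08 |
| Rate ratio 95% CI, dispersion matching SD 0.7 | 0.64–0.92 | 0.66–0.90 |

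**How often the planned difference is detected at SD 0.7.** For the fixed-variance test, power is Φ((0.262 − 1.96 × 0.196)/0.092) = 9% with 46 patients. Simulated integer counts with SD exactly 0.7 gave about 9% with 46 and 17% with 60. Adding a random intercept for four sites left this at 9.0% and 17.3%, with the site variance estimated at zero in every trial. With dispersion estimated and site as a fixed effect, detection was 80.5% and 90.8%. Under no treatment effect, the fixed-variance model rejected in 0.0% of trials and the dispersion-estimated model in 5.2% and 4.7%. The simulations include no true site differences and no early withdrawal, so these rates are illustrative.

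**The case against.** The strongest reply is that nothing decisive is at risk. The t-test is listed first, the Poisson model is only additional, and the objective is exploratory. If the SD is 0.7, the sizing is right and the extra model is merely conservative. If the counts are Poisson, the extra model is right and what remains is ordinary uncertainty about a planning SD. In neither case is a false positive created. All of this stands and sets the severity.

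The software might also estimate a scale parameter. That would remove the excess width, but the SAP does not say so, and fixed variance is the ordinary meaning of the named distribution.

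SAP 5.1 offers another possible explanation: "Only patients with relapses will be analyzed in primary efficacy endpoints". Leaving out zero counts does reduce spread. Yet zero-truncated Poisson counts with means of 2.0 and 2.6 would have SDs of 1.09 and 1.40, still 1.6 and 2.0 times 0.7. Whether that restriction is sound is a separate question.

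Finally, estimating the dispersion does not supply a rule for which analysis governs. That is true; it removes one avoidable cause of disagreement and no more.

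A reader might infer that the trial is underpowered. Under Poisson variance the t-test would have about 26% (33%) power with 46 (60) patients. The documents do not support that conclusion: they do not show that Poisson variance applies, the stated power is already given for SD 0.7, and it reproduces.

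**Conclusion.** The inconsistency is real and its effect is limited to the additional model. Under the plan's own SD, the Poisson model as written has standard errors about 2.1 times too wide and would usually miss the difference the trial was sized to find.

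This rests on two assumptions: that the SD on study is 0.7, as the sample size takes it to be, and that the model fixes the variance at the mean. The documents cannot settle the first and do not state the second. The rates of 9% and 17% do not depend on a random site effect, since leaving it out gives about the same result.

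A reader might also infer that the primary comparison is invalid or the sample size wrong. Neither follows: the t-test stays valid, 46 is correct for the stated inputs, and the model errs on the conservative side. Severity: minor.

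**What to change.** In SAP 11.4.1, state that the count model estimates the dispersion, allowing values below as well as above 1, or uses robust standard errors. A negative binomial model alone would not do, because it does not cover under-dispersion. Report the treatment effect with a 95% confidence interval, both as a difference in means and as a rate ratio. Settle this before unblinding; SAP 4.3 leaves room for it: "The study blind will be broken on completion of the clinical study and after the study database has been locked". Protocol 14.7 and SAP 7 need no change, and no further patients are needed.

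The cost is one model option and one reporting line. If the counts are truly Poisson, estimating the dispersion loses about 1 point of power (about 26% to 25% with 46 patients, 33% to 32% with 60). Robust HC3 errors cost about 3 points more with 46 patients (77% against 80% at SD 0.7; 22% against 25% under Poisson), so estimated dispersion is the cheaper choice at this size.

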10.5 Early Withdrawal Visit

In the case of early withdrawal from the study, activities planned at Visit 3 will be performed, as far as possible.

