# 9.1.4 Methods for Withdrawals and Missing Data

A subject could be discontinued from the study treatment at any time if either the subject, and/or the investigator, and/or Eye Pharma feel that it is not in the subject's best interest to continue the study treatment. The following is a list of possible reasons for study treatment discontinuation:

- Subject withdrawal of consent
- Subject is not compliant with study procedures

Statistical Analysis Plan Version no. 1.0 - 20/07/2020

Protocol Code NORFLO-ORO-16 EudraCT number NA

- Need for the subject to start a systemic anti-inflammatory, immunosuppressive, biologicals therapy for uveitis or for other pathologies
- Adverse event that indicated in the opinion of the investigator that it would be in the best interest of the subject to discontinue study treatment
- Pregnancy
- Protocol violation requiring discontinuation of study treatment
- Missed follow-up
- Eye Pharma requests early study termination.

All subjects who discontinued the study treatment should come back for an early discontinuation visit as soon as possible and then they should be encouraged to complete all remaining scheduled visits and procedures.

All subjects were free to withdraw from participation at any time, for any reason, specified or unspecified, and

Reasonable attempts were made by the investigator to obtain a reason for subject's withdrawals. The reason for the subject's withdrawal from the study was specified in the subject's source documents.

No missing data will be replaced.

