## 11.1 Analysis datasets

All eligible patients who were randomized into the study and received at least one dose of the study product (the Safety Population) will be included in the safety analysis. All eligible patients who were randomized into the study, received at least one dose of the study product and had at least a post-randomization endpoint estimate (the Intention-to-Treat Population) will be included in the efficacy analysis. Primary endpoints will be also analyzed in a modified Intention-to-Treat Population, where the patients with the protocol violations mentioned in the session 10.2 (Protocol Deviations) will be excluded.

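### The step from 46 to 60 patients treats dropouts as leaving the analysis, but the ITT set can keep them with part-year relapse counts and no adjustment for follow-up time, so the 80% power holds only for full 12-month counts

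*Protocol*

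**What the plan says.** Protocol 14.7 sizes the trial on full-year means of 2.6 relapses per patient on placebo and 2.0 on active: "With a statistical power of 80% and a significance level (alpha) of 5% and a common SD of 0.7, 46 patients are needed". It then inflates for dropout: "To take into account a potential dropout rate of 20% over 12 months, 60 patients will be recruited". SAP 7 carries this over: "To take into account a potential dropout rate of 20% over 12 months, 60 patients were recruited".

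Four other provisions decide what happens to a dropout's data:

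- **Analysis set.** SAP 11.1 (also SAP 8.1 and Protocol 14.1) asks for randomisation, one dose and one later estimate. Patients who "had at least a post-randomization endpoint estimate (the Intention-to-Treat Population) will be included in the efficacy analysis". Completing 12 months is not a condition.
- **Withdrawal visit.** Protocol 10.5: "In the case of early withdrawal from the study, activities planned at Visit 3 will be performed, as far as possible". A patient who leaves early can therefore supply the required estimate.
- **Missing data.** SAP 9.1.4: "No missing data will be replaced".
- **Test.** Protocol 14.3 and SAP 11.4.1 compare the number of relapses per patient by Student's t-test, with a Poisson mixed model in addition. No offset, annualised rate or other follow-up adjustment is mentioned for either.

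SAP 5.1 adds that the primary efficacy endpoints are analysed only in patients who relapse.

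**The concern.** The inflation and the analysis describe different data sets. The inflation removes 20% of 60 and leaves 48 patients with full-year counts. The analysis set can hold up to 60 patients, some observed for only part of the year, and treats every count as if it covered the same period.

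A part-year count is lower on average in both arms, so the absolute difference shrinks below 0.6. Mixing short and full counts also raises the SD above the 0.7 used for sizing. The extra 14 patients were added to protect power, yet those who drop out early can reduce it. This happens even when dropout has nothing to do with relapse or treatment. At stake is how far a non-significant primary result can be read as evidence against the planned effect.

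**Working it through.** **Inputs from the documents.** Means 2.6 and 2.0, SD 0.7, alpha 5% (two-sided reproduces the stated size), 20% dropout over 12 months (Protocol 14.7); 30 per arm (Protocol 4.1).

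**Assumptions not in the documents.** Dropout is random and equal in both arms. Every dropout stays in the analysis with no follow-up after leaving. Relapses are spread evenly over the year, so a patient with N relapses in a full year who is observed for a fraction u of it has a Binomial(N, u) count. Site adjustment is ignored.

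**Step 1: the plan's own figure.** Noncentrality = 0.6 / (0.7 × √(2/n)), n per arm.
- n = 22: 2.84, power 79.3%
- n = 23: 2.91, power 81.1%, so 46 in total, as stated
- 46 / 0.8 = 57.5, so 60 is a fair rounding up
- n = 24 (60 less 20%): power 82.8%
- n = 30, all followed for a full year: power 90.4%

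**Step 2: dropouts kept with part-year counts.** With dropout proportion q and full-year mean m:
- mean count M = m(1 − q + q·E[u])
- E[Y²] = (1 − q)(m² + 0.49) + q{m(E[u] − E[u²]) + (m² + 0.49)E[u²]}
- variance = E[Y²] − M²

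Dropout uniform over the year, q = 0.2, E[u] = 1/2, E[u²] = 1/3:
- Placebo: M = 2.6 × 0.9 = 2.34. E[Y²] = 0.8 × 7.25 + 0.2 × (2.6/6 + 7.25/3) = 5.80 + 0.57 = 6.37. Variance = 6.37 − 5.476 = 0.894, SD 0.95.
- Active: M = 2.0 × 0.9 = 1.80. E[Y²] = 0.8 × 4.49 + 0.2 × (2/6 + 4.49/3) = 3.592 + 0.366 = 3.958. Variance = 3.958 − 3.24 = 0.718, SD 0.85.
- Difference 0.54. Pooled SD = √((0.894 + 0.718)/2) = 0.898. Noncentrality = 0.54 / (0.898 × √(2/30)) = 2.33, against a critical t of 2.00 on 58 df. Power is about 63%.

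The same formulas for other cases:

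| Dropout | Difference | Pooled SD | Power, 30 per arm |
|---|---|---|---|
| 20%, uniform | 0.54 | 0.90 | 63% |
| 20%, all at mid-year | 0.54 | 0.86 | 66% |
| 20%, all in first half | 0.51 | 0.99 | 50% |
| 20%, all in second half | 0.57 | 0.78 | 80% |
| 10%, uniform | 0.57 | 0.81 | 76% |

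Simulation with whole-number annual counts of the same mean and SD agrees to within about 2 points. Other ways of modelling a part-year count, with less variation within the patient, give up to 69% for uniform dropout and up to 88% when all leave at 9 months.

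**Step 3: SAP 5.1 taken literally.** Removing patients with no observed relapse takes out many of the shortest follow-ups. Simulated power for 20% uniform dropout is then about 76%.

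**Step 4: relapses per unit of follow-up.** A log-rate comparison with log follow-up time as offset and robust variance, with zero-relapse patients included, gives about 82% for uniform dropout and about 78-84% across the 20% timings above. Type I error is about 5%. Robust variance is needed because the assumed variance (0.7² = 0.49) is far below the Poisson variance (2.0 to 2.6).

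**The case against.** The strongest reply is that nothing in Protocol 14.7 is miscalculated. The 80% is attached to 46 patients, 46 reproduces, and 60 follows from it. That stands. A reader might infer an arithmetic error, or that the trial has 63% power and so a 37% chance of missing the planned effect. The documents support neither. The 63% is one scenario, and several provisions bear on it:

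- No dropout timing is given. If all losses fall in the second half-year, power is about 80%.
- Protocol 11.1 and SAP 9.1.4 encourage patients who stop treatment to complete the remaining visits. Those who do so have full-year counts, and the 10% row shows the gain.
- Protocol 11.2 and 14.7 replace dropouts who start systemic therapy, so the number randomised may exceed 60. Neither document says whether the replaced patient leaves the analysis set.
- The relapse-only rule of SAP 5.1 brings the uniform case to about 76%.
- The endpoint runs from baseline to end of treatment, and the term endpoint estimate is not defined. If a part-year count is treated as missing, dropouts leave the analysis, the inflation is right and power is about 83%.

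These points remove any single power figure for the plan. They do not remove the mismatch. The set definition, the withdrawal visit and the lack of a follow-up term all allow part-year counts into a raw-count test, and nothing excludes them. The relapse-only rule also conflicts with the ITT definition elsewhere in the SAP, so it cannot be relied on as the remedy.

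**Conclusion.** The concern holds as a conditional one. The stated 80% applies to patients with full 12-month counts. For the raw-count t-test on the ITT set, power at 30 per arm depends on when dropouts leave and whether they are followed. With 20% random dropout, all kept and no further follow-up, it is about 63% for uniform timing, from about 50% (all in the first half-year) to about 80% (all in the second). It is about 76% for uniform timing under a literal SAP 5.1, and about 76% at 10% uniform dropout without that rule. Timing, retention in the set and absence of further follow-up are assumptions, and all figures keep the plan's SD of 0.7. They also take dropout as unrelated to relapse, whereas Protocol 7.1 and 10.4 withdraw some patients because of a relapse. This deserves correction, but it is not an error in the printed patient numbers.

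**What to change.** In Protocol 14.3 and SAP 11.4.1, make the primary between-group comparison of relapse number a rate analysis: the Poisson model already planned, with log follow-up time as offset and robust variance. Define follow-up time as running from randomisation to the last date on which relapse status is known. Say that patients without relapses are included, and reconcile SAP 5.1 with SAP 8.1 accordingly. Keep the t-test as supportive. Then align Protocol 14.7 and SAP 7 so that the power statement refers to this analysis. Changing only the sample-size sections would leave a raw-count test as primary, and the sizing would again describe a different analysis.

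If the raw-count t-test stays primary, state in Protocol 14.7 and SAP 7 that 80% applies only to full 12-month counts. Give the conditional range (about 50-80% at 20% dropout, with its assumptions), and say whether a part-year count enters the analysis.

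The first option costs a change of primary test, made before unblinding, using follow-up dates already collected. It needs no more patients. The second costs a few sentences and a less favourable stated power.
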